## **Background**

Immunosuppressive therapy with the calcineurin inhibitors (CI) Cyclosporine (CsA) and Prograf®/tacrolimus (Tac), have radically changed the field of organ transplantation. Ironically, although extensively and effectively used for kidney transplantation and other solid organ transplants, CsA and Tac cause important adverse renal side effects: acute and chronic renal dysfunction, hemolytic-uremic syndrome, hypertension, electrolyte disturbances and tubular acidosis.

Chronic nephrotoxicity from CI has been implicated as a principal cause of post-transplant renal dysfunction  and it is characterized by an irreversible and progressive tubular atrophy, interstitial fibrosis, and focal hyalinosis of small renal arteries and arterioles . Early reports in cardiac transplant recipients by Myers et al.  clearly demonstrated the risk of chronic nephropathy with interstitial fibrosis in patients receiving CsA. Furthermore, reports by Goldstein et al.  and Hornerberger et al.  demonstrated that end-stage renal disease developed in 4.3-6.5% of patients receiving heart transplants after 72-82 months of therapy with CsA. Similarly, liver transplant patients maintained on CI have been shown to develop chronic kidney disease.

In a retrospective analysis, Fisher et al. showed a strong association of early (3 months post-transplant) kidney dysfunction and the risk of developing severe CFR post liver transplant . Gonwa et al.  reported an 18% incidence of severe renal dysfunction at 13 years after orthotopic liver transplant and more important, the development of ESRD was associated with decreased patient survival. The increased mortality in patients with non-renal transplants with chronic renal failure was recently confirmed in a larger population-based cohort analysis . In this study the incidence of chronic renal failure (CRF) in 69,321 patients who received non-renal transplants was 16.5% and CRF was associated with an increase in mortality by a factor of more than four. Risk factors for developing renal failure included: older age, pre-transplant hepatitis C infection, hypertension, diabetes mellitus and chronic exposure to CI.

In renal transplant recipients, complete avoidance of calcineurin inhibitors from the time of renal transplant surgery has been associated with increased incidence of acute cellular rejection. Conflicting data is available regarding the impact of CI avoidance on long term renal allograft function.

We recently completed a retrospective analysis that evaluated renal transplant recipients in which calcineurin inhibitors have been substituted with sirolimus at 1 year post transplant and assessed the risk of rejection, patient and graft loss and renal allograft function. (Please see attached abstract submitted and accepted at the ATC 2007).

From this analysis we concluded that, in a prednisone-free regimen, the conversion from calcineurin inhibitors to sirolimus at 1 yr. post-transplant was not

associated with an increased risk of acute rejection or graft loss. A trend towards a better GFR was noted after conversion from calcineurin inhibitors to sirolimus.

Little is known of the impact of immunosuppressive changes post renal transplant on lymphocytes function.

### **Research Objective**

The aim of the present study is to prospectively investigate the impact of CI conversion (tacrolimus→sirolimus) between 6 and 24 months post-transplant on the incidence of acute cellular rejection, renal allograft function and lymphocytes function.

Primary aim of the study is:

to investigate the impact of CI conversion (tacrolimus→sirolimus) on the incidence of acute cellular rejection.

Secondary aims of the study are:

- i) evaluate whether CI conversion (tacrolimus→sirolimus) contributes positively or negatively on the renal allograft function calculated with e-GFR and proteinuria;
- ii) patient and graft survival ;
- iii) evaluate if CI conversion impacts on lipid profile, incidence of hypertension, malignancies, and opportunistic infections and post-transplant DM;
- iv) evaluate possible modifications of lymphocytes function before and after conversion (tacrolimus→sirolimus)
- v) assess tubular toxicity by evaluating urinary biomarkers

### **Methods**

#### **Immediate Post Transplant Period**

Patients will receive immunosuppressive therapy as follows:

Induction immunotherapy:

- 1) Campath®/alemtuzumab (Anti CD52 humanized monoclonal antibody) (30mg IV), on the day of the kidney transplant,
- 2) methylprednisolone (500 mg IV) on the day of transplant and on day 1 (250 mg IV) and 2 (125 mg IV) post-transplant.

No further steroid will be given post-transplant unless indicated by the following medical conditions: acute renal allograft rejection, renal disease that might require the use of steroids and other systemic diseases such as rheumatoid arthritis (RA), systemic lupus erthematosus (SLE), asthma. Patients

will receive tacrolimus and Cellcept®/mycophenolate mofetil/MMF. The above medication regimen is our standard of care for renal transplant patients, and has been since 2000.

### **Randomization**

For this research study, between 6 and 24 months post-transplant we plan to prospectively randomize 2:1 renal transplant patients to either:

- Continue with tacrolimus and MMF or
- Substitute tacrolimus with sirolimus and continue MMF

A total of 400 pts. are expected to be screened for the randomization and we expect to be able to randomize 275 renal transplant patients into this protocol.

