## **Biopsy**

Chronic nephrotoxicity from calcineurin-inhibitors (CI) has been implicated as a principal cause of post-transplant renal dysfunction and it is characterized by an irreversible and progressive tubular atrophy, interstitial fibrosis, and focal hyalinosis of small renal arteries and arterioles. Furthermore, chronic nephrotoxicity from CI has been documented in all non-renal transplants and the chronic renal failure secondary to the use of CI has been associated with an increase in mortality by a factor of more than four.

The present proposal is to identify those subjects already participating in this study who are willing to undergo a kidney biopsy with the aim of evaluating renal allograft pathology and renal allograft tissue gene expression profiles of the two groups of patients maintained on Tacrolimus/ MMF or switched to SRL/MMF. Performing kidney biopsies on the subjects who consent for the procedure will allow us to address the effect of immunosuppressive modifications on renal allograft pathology at 24 months post randomization. We also plan to obtain renal allograft biopsies at 12 months post-transplant (standard of care) in order to establish a baseline parameter for to compare the 24 month sample. An additional biopsy at 48 months will allow us to examine long term results of graft function. We also plan to obtain renal allograft biopsies to be stored in RNA later to further extend our knowledge on the effect of CI free immunosuppression on gene expression profiles.

Obtaining renal allograft tissue samples at 24 and 48 months post randomization can have potential important ramifications to help explain the mechanisms of fibrosis and tubular atrophy typically associated with CI and the role of CI elimination with the substitution of SRL. All data will then be analyzed comparing gene expression profiles of peripheral blood (Paxgene tubes are routinely collected at the different time points as part of the original study). Based on power analysis, we will perform 24 and 48 months post randomization biopsies in 70% of the total subjects enrolled in the study (approximately 46 subjects from the tacrolimus/MMF group and approximately 93 subjects from the sirolimus/MMF group).

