## **Statistical Analysis**

Once the 2 groups of renal transplant patients are identified, two sample t tests will be used to compare differences in continuous variables between groups; chi square tests will be used to compare differences in discrete variables. Multivariable logistic regression analysis will be also performed to identify the combination of clinical variable that are significantly associated with the development of acute rejection and renal allograft function after conversion from tacrolimus →sirolimus.

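### Rejection is compared across a 6-to-24-month conversion window with no stratification by time since transplant and no prespecified early and late estimates, so an excess confined to part of the window could go unseen

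*Combined protocol and SAP*

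**What the plan says.** The primary aim in Research Objective is "to investigate the impact of CI conversion (tacrolimus→sirolimus) on the incidence of acute cellular rejection", and the same section sets conversion within the 6-to-24-month window. Randomization repeats the window ("between 6 and 24 months post-transplant we plan to prospectively randomize 2:1 renal transplant patients") and gives the target: "we expect to be able to randomize 275 renal transplant patients into this protocol". It mentions no stratification factor and does not describe how the allocation list is built.

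Statistical Analysis is one paragraph. It says that "chi square tests will be used to compare differences in discrete variables", without expressly tying that test to the rejection endpoint. It adds that "Multivariable logistic regression analysis will be also performed to identify the combination of clinical variable that are significantly associated" with rejection and with graft function, and does not name the candidate variables. There is no stratified test, no treatment-by-time term and no early or late estimate.

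The Background offers two facts on timing. The first is that "complete avoidance of calcineurin inhibitors from the time of renal transplant surgery has been associated with increased incidence of acute cellular rejection". The second comes from the centre's own retrospective series in a prednisone-free regimen, where "the conversion from calcineurin inhibitors to sirolimus at 1 yr. post-transplant was not" linked to more acute rejection or graft loss. Neither comes with a rate.

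**The concern.** The window spans 18 months, and the only supporting evidence on conversion in the documents sits at about 1 year. Entrants at month 6 and at month 24 are combined in one comparison of rejection risk. If the effect of conversion is the same throughout, nothing is lost. If it differs, the pooled figure depends on the mix of entry times that recruitment happens to deliver.

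Rejection is both the primary outcome and a harm. A real excess in one part of the window could be reported as no increase across all of it, and readers would apply that statement to patients for whom it is untrue. No planned analysis would show whether this had happened.

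**Working it through.** **Inputs from the documents.** N = 275, ratio 2:1, giving 275 × 2/3 ≈ 183 and 275 × 1/3 ≈ 92. Randomization does not say which arm is larger. The biopsy counts ("approximately 46 subjects from the tacrolimus/MMF group and approximately 93 subjects from the sirolimus/MMF group") imply that it is sirolimus, and I use that. The figure of 275 cannot be reproduced, because no alpha, power, control rate or target difference is given.

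**Assumptions.** Control rejection risk 5% or 10% throughout; an excess of 10 points when conversion is at 6-12 months and none later; two-sided alpha 0.05. None of these comes from the documents. If entry were uniform over the window, the early share would be 6/18 = one third.

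**Step 1: dilution.** Pooled excess = early excess × early share.

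- 20% early: 10 × 0.2 = 2 points
- 50% early: 10 × 0.5 = 5 points
- 80% early: 10 × 0.8 = 8 points

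The same formula applies to an excess confined to late conversion, using the late share.

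**Step 2: what each comparison could detect.** Power of the usual two-proportion normal test, for the 10-point early excess:

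| Control risk | Early share | Pooled excess (points) | Power, pooled test | Power, early stratum alone |
|---|---|---|---|---|
| 5% | 1/3 | 3.3 | 15% | 26% |
| 5% | 1/2 | 5.0 | 27% | 39% |
| 10% | 1/3 | 3.3 | 11% | 20% |
| 10% | 1/2 | 5.0 | 20% | 30% |

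Power is low everywhere, but the pooled test is the weaker of the two in each row. For reference, the pooled test reaches 80% power only at an overall excess of about 11 points (5% control risk) or 14 points (10% control risk).

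**Step 3: precision of the stratum results.** Take half the subjects early (46 tacrolimus, 91.5 sirolimus), control risk 10% and early sirolimus risk 20%.

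- Early SE = √(0.10×0.90/46 + 0.20×0.80/91.5) = 0.061; 95% half-width 1.96 × 0.061 ≈ 12 points.
- Late SE = √(0.10×0.90/46 + 0.10×0.90/91.5) = 0.054.
- SE of the early-minus-late difference = √(0.061² + 0.054²) ≈ 0.082; half-width about 16 points.

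The interaction is therefore estimated less precisely than either stratum effect.

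**Step 4: chance imbalance.** Assume simple randomisation and half the subjects early. The SE of the between-arm difference in early share is √(0.25 × (1/92 + 1/183)) = 0.064, and 1.96 × 0.064 = 0.125, or about ±12.5 points. If underlying rejection risk differs by 5 to 10 points between early and late entrants, an imbalance that large moves the result by 0.125 × 5 ≈ 0.6 to 0.125 × 10 ≈ 1.2 points. That is small beside the dilution in Step 1.

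**The case against.** The strongest reply is that the trial asks about conversion anywhere in the window, and randomisation makes the pooled comparison an unbiased answer to that question. This stands. Separate early and late estimates are an addition; they do not repair a biased analysis.

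Four stronger readings are tempting, and the documents do not support them.

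- *The Background proves that timing governs the risk.* It contrasts avoidance from surgery, which lies outside the window, with substitution at 1 year. These are different strategies from different sources, and no gradient within 6-24 months is given.
- *Months 6-12 are the one untested part.* The months well after 1 year are equally without evidence.
- *There will be no adjustment.* The logistic regression might include time since transplant. What can be said is that none is specified. A main-effect covariate would in any case not reveal an effect that varies with time.
- *Time since transplant will be unavailable because Data Collection does not list it.* It has to be known to apply the window, and it follows from the transplant and randomisation dates.

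It is also fair to object that the 10-point excess is chosen for illustration and that the fourfold spread from 2 to 8 points merely reflects the chosen shares of 20% and 80%.

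**Conclusion.** The point holds as a design and analysis gap of moderate weight. One wide window is randomised without stratification, and nothing prespecified examines whether the rejection effect varies across it. The dilution formula is exact when the excess is confined to one part of the window; the 2-to-8-point figures and the power values rest on assumed rates, an assumed excess and assumed entry shares. A reader might infer that the trial's main result is biased or that early conversion has been shown to be harmful. Neither follows: the pooled estimate is a valid average, chance imbalance is worth about 1 point at most under the rates assumed, and the documents contain no data on early conversion. What is missing is the means to tell whether that average applies to the whole window.

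**What to change.** In Randomization, stratify the allocation list by time since transplant at randomisation: 6-12 versus >12-24 months. If enrolment has begun, leave the allocation as it is and make only the analysis changes.

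In Statistical Analysis:

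1. Name the rejection comparison stratified by this factor (Mantel-Haenszel) as primary.
2. Report the rejection risk difference with its 95% confidence interval in each stratum.
3. Prespecify a treatment-by-time-since-transplant interaction test, labelled as supportive.
4. State that the overall stratified comparison carries the conclusion and that stratum results will not be used to select it.

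Items 2 and 3 are essential to the purpose: stratified allocation and a Mantel-Haenszel test alone still give a single pooled answer.

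The cost is one two-level factor and a few lines of text, with no added subjects, visits or tests. The drawback is imprecision. With 275 subjects the stratum intervals will be wide, and a non-significant interaction will not establish that the effect is uniform. The text should say so.

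### The 2:1 randomisation does not say which arm gets the two shares, the biopsy counts point the opposite way from the listed order, and those counts are 50.5%, not 70%, of the planned 275.

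*Combined protocol and SAP*

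**What the plan says.** Under Randomization, the protocol states: "between 6 and 24 months post-transplant we plan to prospectively randomize 2:1 renal transplant patients to either" of two bulleted options. The first is "Continue with tacrolimus and MMF or" and the second is "Substitute tacrolimus with sirolimus and continue MMF". Neither bullet carries a share of the ratio, and no arm sizes are given. On the total it says "we expect to be able to randomize 275 renal transplant patients into this protocol". Subject Selection and Withdrawal and Subject Recruitment and Screening repeat the 275 without splitting it by arm.

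The Biopsy section is the only place with numbers by arm. It says "we will perform 24 and 48 months post randomization biopsies in 70% of the total subjects enrolled in the study" and gives these as "approximately 46 subjects from the tacrolimus/MMF group and approximately 93 subjects from the sirolimus/MMF group". It attributes this to a power analysis that the document does not show. The Statistical Analysis section contains no sample size or allocation statement.

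**The concern.** A reader who meets a ratio followed by a list normally matches the two in order. Here that gives two tacrolimus subjects for each sirolimus subject. The biopsy counts have twice as many sirolimus as tacrolimus subjects, so they suggest the reverse. Someone setting up the randomisation from the Randomization section alone could build the opposite allocation from the one assumed in the Biopsy section.

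The primary aim is the effect of conversion on acute cellular rejection, so the direction decides how many subjects are converted and how precisely rejection after conversion can be estimated. It also decides how many subjects need the weekly laboratory tests during conversion, and how large a share of each arm must agree to biopsy.

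There is a second problem. The biopsy counts are tied to a stated percentage of enrolment, so they can be checked against 275, and they do not fit. Settling the direction alone would leave that mismatch in place.

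**Working it through.** **Inputs.** From Randomization: ratio 2:1 with no direction, and 275 expected to be randomised. From Biopsy: 70% of all enrolled, about 46 tacrolimus and about 93 sirolimus.

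**Step 1: reproduce the plan's biopsy figure.**
- Stated total: 46 + 93 = 139.
- 70% of the stated enrolment: 0.70 × 275 = 192.5. The stated total is not reproduced.
- Fraction actually planned: 139/275 = 50.5%.
- Enrolment at which 139 is 70%: 139/0.70 = 198.6, about 199.
- At 199 and 1:2 tacrolimus to sirolimus: 0.70 × 199/3 = 46.4 and 0.70 × 199 × 2/3 = 92.9. These round to the stated 46 and 93.

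The counts are therefore what 70% of about 199 subjects gives at 1:2. That they were derived this way is an inference from the fit; the document does not say so.

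**Step 2: direction implied by the counts.** 93/46 = 2.02 sirolimus subjects per tacrolimus subject.

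**Step 3: arm sizes at 275 under each direction.** The larger arm is 275 × 2/3 = 183.3 and the smaller is 275/3 = 91.7.

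| | Listed order (2:1 for tacrolimus) | Reverse (1:2 tacrolimus to sirolimus) |
|---|---|---|
| Tacrolimus/MMF | about 183 | about 92 |
| Sirolimus/MMF | about 92 | about 183 |
| 70% of tacrolimus arm | about 128 | about 64 |
| 70% of sirolimus arm | about 64 | about 128 |
| Stated 46 as share of tacrolimus arm | 46/183.3 = 25% | 46/91.7 = 50% |
| Stated 93 as share of sirolimus arm | 93/91.7 = 101% | 93/183.3 = 51% |

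Only the reverse direction gives about the same fraction in both arms. Neither direction gives 46 and 93 as 70% of arms that sum to 275.

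**Step 4: what the direction changes.** The number converted differs by about 183 − 92 = 91. The document gives no expected rejection rate, so I assume a range. The 95% half-width for the rejection proportion in the sirolimus arm is 1.96 × √(p(1 − p)/n).

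| Assumed rate | n = 92 | n = 183 |
|---|---|---|
| 5% | 4.5 points | 3.2 points |
| 10% | 6.1 points | 4.3 points |
| 20% | 8.2 points | 5.8 points |

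The between-arm difference is much less affected. If the two risks are similar, its variance depends on 1/92 + 1/183, which is the same in either direction.

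**The case against.** The strongest reply is that this is an ambiguity and not a contradiction. The Randomization section never ties a number to an arm, and matching a ratio to list order is a convention. An allocation of two sirolimus to one tacrolimus satisfies both sections, and the Biopsy section can be read as the clarification. That stands. A reader might infer that the two sections cannot both be followed, but this is true only if the listed order is assumed.

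A reader might also infer from the 101% that the plan asks for more sirolimus biopsies than there would be sirolimus subjects. The document does not support that as a finding. The excess is 93 against 91.7, the count is given as approximate, 275 is an expectation, and the comparison again assumes the listed order. It also divides a count that fits about 199 subjects by an arm built on 275.

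Finally, the 70% is stated for the total, biopsies depend on consent, and the power analysis is not shown. An equal fraction per arm is therefore a plausible reading and not a stated rule. This weakens the inference about direction somewhat. It does not touch the mismatch between 139 and 70% of 275, which needs only the total.

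What remains is that a randomised trial's allocation should not have to be inferred from sub-study counts, least of all from counts that disagree with their own percentage.

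**Conclusion.** The point holds as two linked defects. First, the direction of the 2:1 ratio is not stated. The listed order suggests about 183 tacrolimus and 92 sirolimus, and the biopsy split suggests about 92 and 183. The second is probably what was intended, since 46 and 93 follow a 1:2 split closely, but the document does not confirm it. Second, the biopsy total of 139 is 50.5% of 275 and not 70%. It falls short of 192.5 by 53.5 subjects and matches 70% only at an enrolment of about 199.

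The arm sizes assume that 275 are randomised and that the ratio is met exactly. The precision figures assume rejection rates of 5% to 20%, which are not from the document. The second defect needs no assumption beyond reading the total enrolled as the expected 275. The generated allocation list was not available, so nothing here shows that subjects were or would be allocated in the wrong direction.

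**What to change.** 1. In Randomization, state the ratio with the arms named and the expected numbers. If the Biopsy section reflects the intent: 1:2, tacrolimus/MMF to sirolimus/MMF, about 92 and 183 of 275.
2. Check that the allocation list was generated in that direction.
3. Restate the Biopsy section so that percentage, per-arm counts and enrolment agree, and check the result against the power analysis it cites. There are three ways to do this:
   - Keep 46 and 93 and describe 139 as about 50% of 275. This adds no biopsies.
   - Keep 70% of 275, which at 1:2 is about 64 tacrolimus and 128 sirolimus. That is 64 + 128 − 139 = 53 more subjects biopsied at each of the two time points.
   - If about 199 is the true expected enrolment, correct the 275 wherever it appears and give arm sizes of about 66 and 133 (199/3 and 199 × 2/3).

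On the first route the cost is a few sentences and a check of the list. The second adds procedures for subjects and workload. The third changes the trial's stated size and would need its own justification.
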